7. ANALYSIS POPULATIONS

7.1. Intent-to-Treat (ITT) Population

The ITT population includes all subjects who are randomized. Subjects in the ITT population will be analyzed according to the randomized assignment, regardless of the actual treatment received. All baseline characteristics will be summarized based on the ITT population. The primary analyses of the primary efficacy endpoint will be based on the ITT population.

7.2. Safety Population

The safety population will contain all subjects who are randomized and receive at least one study drug injection. Subjects will be grouped according to their actual treatment received, not according to their randomization assignment. Subjects treated with any VM202 will be grouped in the VM202 group; subjects never treated with any VM202 will be grouped in the placebo group. All safety summaries will be based on the safety population.

7.3. Modified Intent-to-Treat (mITT) Population

The mITT population includes all subjects randomized that meet the following criteria:

- Received any study drug injections
- Had at least one post-baseline wound assessment
- Have no safety or efficacy parameter results prior to dosing on Day 0 that would have made the subject ineligible for participation if the results had been known or disclosed at Screening. This determination will be made in a blinded fashion by the Clinical Data Review Committee (CDRC, members to be determined) prior to analyses.

Subjects will be grouped based on the randomly assigned treatment, not the actual treatment received. The mITT population will be used in the sensitivity analyses for the primary efficacy endpoint.

7.4. Per Protocol (PP) Populations

The first Per Protocol population is a subset of the mITT. It includes all mITT subjects who meet the following criterion:

• Have not used the protocol-specified prohibited concomitant medications such as COX-2 inhibitor drug(s) or non-specific COX-1/COX-2 inhibiting NSAIDS, anti-VEGF agents (e.g., Lucentis[®], Avastin[®], Eylea[®]), steroids (except inhaled steroids or ocular steroids), Regranex[®] gel (becaplermin), larval debridement, skin substitutes (e.g., Dermagraft[®], Apligraf[®]), hyperbaric oxygen therapy, hydrotherapy, negative pressure wound therapy, or electrical stimulation therapy which may affect the wound healing. The use and effect of protocol-specified prohibited concomitant medications will be determined by the CDRC in a blinded fashion prior to analyses.

The second Per Protocol population is a further subset of the mITT. It includes all subjects in the first PP population who also meet all of the following criteria:

- Meets major protocol eligibility criteria determined by the CDRC in a blinded fashion prior to analyses
- Received all injections based on the randomized treatment
- Maintained standard of care for their wounds for the duration of the study, as follows:
 - O Surgical debridement of necrotic tissue or devitalized tissue
 - Use of appropriate off-loading when ambulating
 - o Maintenance of moist wound environment
- Additional criteria, if any, established by the CDRC before unblinding of the randomization code

The PP populations will be used in the sensitivity analyses for the primary efficacy endpoint.

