3.4.4. STANDARD OF CARE

At screening, standard of care for all wounds on the target foot will be initiated that will continue for the duration of the study/until the ulcer has completely healed:

- Surgical debridement of necrotic tissue or devitalized tissue
- Use of appropriate off-loading when ambulating
- Maintenance of a clean and moist wound environment

Detailed instructions can be found in Appendix 4.

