3.5. STUDY COMPLETION

3.5.1. COMPLETED SUBJECTS

Each subject in the study will be considered completed when all assessments through 7 months have been performed in accordance with the study protocol.

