Appendix 4. Standardized Wound Care

Protocol VMNHU-003/I CONFIDENTIAL Starting at screening, wound care will be standardized as follows for the duration of the study/until the ulcer has completely healed:

Surgical debridement of necrotic tissue or devitalized tissue

The extent of debridement is based on the wound and will be determined by the Principal Investigator or his/her representative based on his/her standard of care.

Maintenance of a clean and moist wound environment

- A wound cleanser will be used to maintain a clean environment; specifically, Puracyn[®] Plus (Innovacyn, Inc, Rialto, CA) will be provided to the sites for use in study subjects in order to increase compliance and standardization
- A non-medicated, absorbent hydrocellular foam dressing will be used. Specifically, ALLEVYN Gentle (Smith & Nephew, London, UK) with a soft gel adhesive which minimizes trauma to the wound at dressing change will be provided to the sites for use in study subjects in order to increase compliance and standardization.

Note: in subjects with multiple ulcers on the target foot, all ulcers will be cleansed with Puracyn[®] Plus and dressed with ALLEVYN Gentle in order to maintain standardized care for the entire target foot.

Use of appropriate off-loading when ambulating

Removable footwear will be used for ulcer offloading. Choice of footwear will depend on the location of the ulcer. A boot should be considered for plantar ulcers; an off-loading postoperative shoe should be considered for all ulcers located elsewhere below the malleolus. Examples adapted from: *Consensus Recommendations on Advancing the Standard of Care for treating Neuropathic Foot Ulcers in Patients with Diabetes*, Snyder, RJ (2010)⁵⁸ are provided in Table 8.

Protocol VMNHU-003/I CONFIDENTIAL Helixmith Co., Ltd
Page 100 of 122

Table 8. Removable footwear options for off-loading by ulcer location

		Removable Footwear Offloading Options									
Ulcer location	CROW Boot	Prefabrica ted Walker	DH Offloading Walker	IPOS Shoe	Ortho Wedge	PostOp Shoe	Healing Sandals	Reverse IPOS	L'nard Splint	PTB Brace	MABAL Shoe
Dorsal Digit						х					
Plantar Digit	Х	Х	Х	Х	Х		Х				Х
Plantar Metatarsal	х	Х	Х	х	х		Х				Х

				Remov	vable Foot	wear Off	loading Opt	tions			
Ulcer location	CROW Boot	Prefabrica ted Walker	DH Offloading Walker	IPOS Shoe	Ortho Wedge	PostOp Shoe	Healing Sandals	Reverse IPOS	L'nard Splint	PTB Brace	MABAL Shoe
Medial Metatarsal	Х	X	X	Х	X		Х				Х
Lateral Metatarsal	х	Х	Х	Х	X		Х				х

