3. STUDY DESIGN

This is a phase III, randomized, double-blind, placebo-controlled, multicenter, 7-month study designed to assess the safety and efficacy of intramuscular injections of VM202 in the calf of diabetic patients with chronic nonhealing foot ulcers and concomitant PAD. Subjects with confirmed PAD and diabetes aged \geq 18 years to \leq 80 years diagnosed with nonhealing foot ulcers will be screened for study eligibility after giving informed consent.

At Screening, standard of care will be initiated that will continue for the duration of the study, as follows:

- Surgical debridement of necrotic tissue or devitalized tissue
- Use of appropriate off-loading when ambulating
- Maintenance of moist wound environment

Three hundred patients (from up to 30 study centers) who meet the eligibility criteria will be randomized in a 2:1 ratio to one of two treatment groups: 200 patients with VM202 (16 mg) plus standard of care or 100 subjects with placebo plus standard of care, respectively. Safety will be monitored throughout the study by an independent Data Safety Monitoring Board (DSMB, Section 8.5).

Patients will receive intramuscular injections in the ipsilateral calf of the affected foot with the target ulcer of either VM202 or placebo on Day 0, Day 14, Day 28, and Day 42 as follows:

Treatment: Days 0, 14, 28, and 42

TREATMENT]	DOSE VM20	FINAL DOSE		
GROUP	DAY 0	DAY 14	DAY 28	DAY 42	VM202 (mg)
VM202	4	4	4	4	16
Placebo	0	0	0	0	0

0 indicates injections of Placebo

VM202 will be delivered in a solution of 0.5 mg VM202 / mL. All subjects will receive sixteen (16) 0.5-mL intramuscular injections of VM202 or placebo at each injection visit.

The schedule of study visits and the clinical parameters that will be measured at the visits are summarized in Table 1 to Table 3 below.

The subjects' target ulcer will be evaluated by photograph, surface area, depth, perimeter and volume measurements. Subjects must have a non-healing ulcer on Day 0 that meets study entry inclusion criterion # 5 and does not meet exclusion criterion #6 to be eligible for study participation. Subjects will continue to come to the clinic once a week for dressing changes and wound assessment until the ulcer has healed or study exit, whichever comes first. Measurement of the target ulcer will be performed at each follow-up visit until complete wound closure or study exit.

Further details on the study procedures and conduct are provided in the protocol.

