5.3.2. Definitions of Efficacy Endpoints

Complete Wound Closure

Defined as skin 100% re-epithelization without drainage or dressing at any time during the study. Complete wound closure will be assessed by the investigator at the sites and 100% reconciled with the ARANZ data, when possible. The primary analysis will be based on the eCRF page "Photography and Measurement of Ulcer in Target Leg".

Wound Volume, Wound Perimeter, Wound Area, and Wound Depth

The target wound's volume, perimeter, area, and depth will be measured using ARANZ Silhouette products at baseline and every scheduled post-baseline visit until wound closure.

Formation of New Foot Ulcer

Defined as a newly formed non-healing or poorly healing full-thickness wound, below the ankle on the target foot; these will be identified solely based the AE data provided by the site. The AE verbatim term will be scanned for the text "ULCER" and for "LEFT" vs. "RIGHT". The side will be matched with the target limb side from the eCRF and, if no information on site is present, it will be assumed that the new ulcer is on the target limb.

Major amputation

Defined as an amputation of the lower extremity above the ankle; these will be identified based on a blinded review of the AE data. The affected leg identified in the verbatim term on the AE electronic case report form (eCRF) and target foot noted on Physical Exam eCRF will be used to determine if the major amputation was in the target limb. These amputations will be noted in the clinical study report (CSR).

Minor amputation

Defined as an amputation of a foot or any parts of a foot such as toes; these will be identified based on a blinded review of the AE data. The affected leg identified in the verbatim term on the AE eCRF and target foot noted on Physical Exam eCRF will be used to determine if the minor amputation was in the target limb. These amputations will be noted in the CSR.

Cardiff Wound Impact Questionnaire (CWIQ)

The CWIQ is a patient-reported outcome measure designed to assess the impact of leg and diabetic foot ulcers on patient health-related quality of life (HRQoL). There are 3 domains/subscales:

- well-being (7 items, graded on a 5-point scale [1 = strongly disagree to 5 = strongly agree])
- physical symptoms and daily living (24 items, graded on a 5-point scale [1 = not at all to 5 = always])

• social life (14 items, graded on a 5-point scale [1 = not at all/not applicable to 5 = very])

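### PP2's wound-care criterion runs to study end with no stop at healing: read literally, it excludes 4-month responders and counts lapses after the 4-month visit

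*SAP*

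**What the plan says.** **PP2 criterion.** SAP 7.4 requires that subjects "Maintained standard of care for their wounds for the duration of the study, as follows": debridement, off-loading and "Maintenance of moist wound environment". Protocol 6.2.4.2 has the same criterion. Neither mentions healing.

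**Length of the study.** Protocol 3.5.1: "Each subject in the study will be considered completed when all assessments through 7 months have been performed". That is Day 210.

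**How long the care lasts.** The documents give two answers.
- Protocol 3.4.4 says that it "will continue for the duration of the study/until the ulcer has completely healed". Appendix 4 agrees: "wound care will be standardized as follows for the duration of the study/until the ulcer has completely healed".
- SAP 3 gives no stop at healing: "standard of care will be initiated that will continue for the duration of the study, as follows". The Protocol synopsis and Protocol 3.2 read the same way.

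Weekly clinic visits for dressing changes end at healing or study exit, whichever is earlier (Protocol synopsis and 3.2, SAP 3).

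**Closure.** SAP 5.3.2: "Defined as skin 100% re-epithelization without drainage or dressing at any time during the study".

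**Use of PP2.** The per-protocol sets serve sensitivity analyses of the primary endpoint, closure by the 4-month follow-up, tested with Fisher's exact test (SAP 7.4, 9.4.1.2.2). The primary analysis uses the ITT population (SAP 9.4.1.1).

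**Who decides.** Within PP2, the CDRC is named for major eligibility criteria and for any additional criteria. No one is named for the wound-care criterion.

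**The concern.** A per-protocol set should be defined by adherence, not by outcome. Here a subject who reaches the endpoint loses the dressing, and with it the ability to meet the moist-wound requirement for the rest of the study. Applied to the letter, the rule excludes subjects because they responded, and it excludes more from the arm that heals more.

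The window is also too long for its purpose. An unhealed subject who stops off-loading in month 6 has a 4-month result that was already settled, yet would leave the set.

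SAP 9.4.1.2 presents the sensitivity analyses as a demonstration that the primary result is robust. A set that drops responders by definition cannot serve that purpose. If the rule is instead applied loosely, the set analysed is not the one written down.

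**Working it through.** **Step 1: the two rules side by side.** Take a subject whose target ulcer is closed at Day 120, the latest nominal day that counts for the primary endpoint.

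- Days from then to study end: 210 - 120 = 90, and more for an earlier closure.
- Under Protocol 3.4.4 and Appendix 4, care may end at healing, so the subject complied in full.
- Under the PP2 wording, care must run the further 90 days. A closed ulcer has no dressing, so the moist-environment item fails.

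The same holds for every 4-month responder. A subject first closed at Day 210 would not be removed. A subject first closed between the two visits would be removed as a 4-month non-responder; the documents give no rate from which to count these.

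**Step 2: the plan's own figures.** The plan states no figure for PP2. The responder rates come from SAP 6 (VM202 50% to 60%, placebo 20% to 30%). Exact enumeration of the two-sided 0.05 Fisher test with 200 and 100 subjects reproduces all nine entries of SAP Table 4 to within 0.02. The largest gap is at 50% versus 30%: 0.918 computed, 0.898 stated. The power table is not in dispute.

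**Step 3: literal PP2 at the planned size**, before any other exclusion. Responders = arm size × rate; remaining = arm size - responders; share removed = all responders / 300.

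| VM202 / placebo rate | Responders | Remaining under literal PP2 | Share removed | Fisher p, responders kept | Fisher p, literal PP2 |
|---|---|---|---|---|---|
| 50% / 30% | 100, 30 | 100, 70 | 130/300 = 43% | 0.0013 | 1 |
| 50% / 20% | 100, 20 | 100, 80 | 120/300 = 40% | 4.4 × 10^-7 | 1 |
| 60% / 30% | 120, 30 | 80, 70 | 150/300 = 50% | 1.4 × 10^-6 | 1 |
| 60% / 20% | 120, 20 | 80, 80 | 140/300 = 47% | 3.4 × 10^-11 | 1 |

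The p-values are for the expected counts. In the literal set both arms have 0 responders, so p = 1 whatever the true effect.

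**Step 4: the subjects actually enrolled.** SAP 1 gives 7 + 5 + 16 + 16 = 44. The documents give no split by arm. At 2:1 it would be about 29:15, which is an assumption.

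- VM202 responders: 29 × 0.50 to 0.60 = 14.5 to 17.4
- Placebo responders: 15 × 0.20 to 0.30 = 3.0 to 4.5
- Total: 17.5 to 21.9, or about 18 to 22 of 44

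This is the ceiling for 4-month responders lost: literal reading, assumed split, planning rates.

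**The case against.** **The sensible reading.** The criterion concerns care of the subjects' wounds. Protocol 3.4.4 and Appendix 4 let that care end at healing, and debridement and moisture have no object once the wound is closed. On that reading a subject treated until closure did maintain standard of care and stays in PP2. This stands, and it makes the problem a drafting gap. It does not close the gap, because PP2 omits the healing limit and names no one to apply the criterion. The CDRC's power to add criteria cannot relax an existing one. SAP 8.1 does send questionable situations to the CDRC for blinded review, but SAP 8.5 also allows the DSMB, which sees unblinded safety tables, to be asked about deviations that affect the per-protocol sets. An outcome-linked criterion should not depend on interpretation.

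**Care does not always end at closure.** This also stands. The synopsis, Protocol 3.2 and SAP 3 do not stop care at healing, and care covers all wounds on the target foot, so a subject with another open ulcer may still be under care. However, more than one ulcer on the target foot was an exclusion until version G (SAP 1), and 7 + 5 + 16 = 28 of the 44 enrolled under earlier versions.

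**PP1.** A reader might infer that PP1's prohibited-treatment condition has the same fault. The documents do not support that: SAP 7.4 has the CDRC judge, blinded, both the use and the effect of those treatments, so it can already disregard use that could not have affected the outcome. Ending that window at closure would also make it depend on the outcome.

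**The remedy is not neutral either.** Ending the PP2 window at closure gives early closers less time in which to deviate. That is true, and it is a much smaller dependence than excluding every closer.

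**Conclusion.** The point holds as a defect in the PP2 wording. As written, the criterion ties membership to the outcome and extends about three months beyond the endpoint that the set is used to analyse. The second effect needs no strained reading: a lapse after Day 120 counts against an unhealed subject under any reading of the text.

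A reader might infer that PP2 will in fact contain no responders, or that the trial's efficacy result is biased. The documents support neither. The removal of 40% to 50% at the planned size, and of 18 to 22 among the 44 enrolled, describes only the literal extreme, which a blinded committee would be unlikely to apply. It rests on planning rates and, for the 44, on an assumed split. The wound-care criterion does not touch the ITT primary analysis, mITT or PP1, and SAP 8.4 treats sensitivity analyses as supportive. The correction is worth making because it is cheap and because PP2 cannot support robustness while its definition is open to this reading.

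**What to change.** 1. In SAP 7.4 and Protocol 6.2.4.2, state that the PP2 wound-care criterion is assessed from Screening until complete closure of the target ulcer or the 4-month visit, whichever comes first, and that later events do not affect PP2 membership.
2. State that the CDRC applies this criterion blinded and finalises the set before unblinding.
3. Reconcile the statements on how long care lasts: Protocol synopsis, Protocol 3.2 and SAP 3 on one side, Protocol 3.4.4 and Appendix 4 on the other. Which of them should govern patient care is for the sponsor to settle. Items 1 and 2 concern only membership of an analysis set.
4. Leave the PP1 condition as it is.

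The cost is a sentence or two in each document and a date check in the CDRC's listings. There are two small downsides: subjects with late lapses stay in PP2, which suits a 4-month endpoint, and early closers have a shorter period in which to deviate, which should be acknowledged when PP2 is reported.

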7.5. Subgroup Analysis Subsets

The primary and exploratory efficacy endpoints will be evaluated as described in Section 9.4.2 for the following subgroup subsets; except where noted, these subsets are based on the categories of the covariates described in Section 4.5.

- Wound location (weight-bearing [sole of the foot], and not weight-bearing [all other locations])
- Age (\leq median and > median)
- Baseline wound area (≤ median and > median)

These subgroups will be re-examined and may be recategorized or eliminated (if only two categories) due to small sample size (if there are < 10% of subjects within each subgroup) before unblinding for analysis.

The treatment by subgroup interaction will be examined and tested as described in Section 9.4.2. The subgroup analyses will be exploratory in nature and will be conducted in the ITT population.

8. DATA HANDLING

8.1. General Principles of Data Handling

Data screening will be conducted in a blinded fashion periodically during the conduct of the study. The objective of the data screening is to assess the quantity, quality, and statistical characteristics of the data relative to the requirements of the planned analyses. Any questionable values or situations will be reported to the CDRC for blinded review and confirmation.

Except as noted below, the data source for all safety and efficacy endpoints will be the study's Electronic Data Capture database (DATATRAK). Extracts from the Interactive Web Response System used for randomization will be the data source for the randomized treatment. The actual treatment received will be determined from the randomized treatment with adjustments based

on externally noted protocol/procedural deviations. All wound measurement data will come from the ARANZ Medical study-specific database, and pharmacokinetic data (HGF serum levels and copies of VM202 in whole blood) will be provided by Inc.

8.2. Visit Windows

Data at each scheduled follow-up visit will be analyzed according to the nominal visit identified on the data record. In case of multiple different visits identified with the same nominal visit, the visit with the visit date closest to the target days of each protocol-specified visit schedule (Table 5) will be used for the efficacy analyses of exploratory endpoints assessed at specific months. For visits with the same distance to the target days, the later nominal visit record will be used. Data from the other visits (if any) will be provided in data listings.

Table 5 Target Day and Month Descriptor

	1 st INJECTION	2 ND INJECTION	3 RD INJECTION	4 TH INJECTION	DAY 60	DAY 74	DAY 90	DAY 120	DAY 210
TARGET DAY	0	14	28	42	60	74	90	120	210
FOLLOW-UP MONTH	-	-	-	-	2	2.5	3	4	7

Data from 'weekly wound assessment and dressing change', 'confirmation of ulcer healing', 'early withdrawal', and any unscheduled study visits will be used in addition to the scheduled target day visits to determine efficacy endpoints that are the response rate by a given follow-up visit (e.g., the primary efficacy endpoint) or a time to event endpoint (e.g., time to complete wound closure).

8.3. Unmasking of Randomization Codes

For the final data analyses, the randomization code will be unmasked to the project team after all the data queries related to the efficacy and safety outcomes have been resolved and the corresponding data revisions have been completed in the database.

The randomization code for individual safety data will be unmasked to the DSMB members and the team that will prepare the unblinded summary tables for the DSMB meetings. However, in order to prevent bias, the unblinded detailed safety data summaries and listings will not be shared with the sponsor management team, the CDRC, the study sites, or the team that is monitoring the clinical data collection.

The randomization code will be unmasked to the team that will prepare the interim futility analysis described in Section 10. These unmasked primary efficacy results and the conditional power will be shared with unblinded Regulatory and Clinical advisors (to be named) and may be shared with the sponsor management team. However, in order to prevent bias, the unmasked interim results will not be shared with the CDRC, the study sites, or the team that is monitoring the clinical data collection.

